### Serum inflammatory biomarkers

Serum will be obtained at baseline and during treatment and assessed for resolution of elevated levels of IFN-inducible chemokines.

## 6.5 Adverse Events

An *Adverse Event (AE)* is defined as any new untoward medical occurrence or worsening of a pre-existing medical condition in a patient or clinical investigation subject administered an investigational (medicinal) product and that does not necessarily have a causal relationship with this treatment. An AE can therefore be any unfavorable and unintended sign (including an abnormal laboratory finding, for example), symptom, or disease temporally associated with the use of investigational product, whether or not considered related to the investigational product.

### 6.5.1 Serious Adverse Events

A *Serious Adverse Event (SAE)* is any untoward medical occurrence that at any dose:

- 1) results in death is life-threatening (defined as an event in which the subject was at risk of death at the time of the event;
- 2) it does not refer to an event which hypothetically might have caused death if it were more severe)
- 3) requires inpatient hospitalization or causes prolongation of existing hospitalization (see note below for exceptions)
- 4) results in persistent or significant disability/incapacity is a congenital anomaly/birth defect is an important medical event (defined as a medical event(s) that may not be immediately life-threatening or result in death or hospitalization but, based upon appropriate medical and scientific judgment, may jeopardize the subject or may require intervention [eg, medical, surgical] to prevent one of the other serious outcomes listed in the definition above.)

Examples of such events include, but are not limited to, intensive treatment in an emergency room or at home for allergic bronchospasm; blood dyscrasias or convulsions that do not result in hospitalization.) Potential drug induced liver injury (DILI) is also considered an important medical event. (See Section 6.6 for the definition of potential DILI.)

Suspected transmission of an infectious agent (eg, pathogenic or nonpathogenic) via the study drug is an SAE.

All pregnancies, regardless of outcome, must be reported to BMS, **including pregnancies that occur in the female partner of a male study subject. All pregnancies must be followed to outcome.** See Section 7.6 for instructions on reporting pregnancies.

Although pregnancy, overdose, cancer, and potential drug induced liver injury (DILI) are not always serious by regulatory definition, these events must be handled as SAEs and should also be reported to BMS in an expedited manner, as described in Section 7.2.

**NOTE:** The following hospitalizations are not considered SAEs in BMS clinical studies:

- 1) a visit to the emergency room or other hospital department lasting less than 24 hours that does not result in admission (unless considered an “important medical event” or a life-threatening event)
- 2) elective surgery planned before signing consent admissions as per protocol for a planned medical/surgical procedure routine health assessment requiring admission for baseline/trending of health status (eg, routine colonoscopy)
- 3) medical/surgical admission for purpose other than remedying ill health state that was planned before study entry. Appropriate documentation is required in these cases.
- 4) admission encountered for another life circumstance that carries no bearing on health status and requires no medical/surgical intervention (eg, lack of housing, economic inadequacy, caregiver respite, family circumstances, administrative).

### **6.5.2 Nonserious Adverse Events**

Nonserious adverse events are all adverse events that are not classified as SAEs.

## **6.6 Assignment of Adverse Event Intensity and Relationship to Abatacept**

All adverse events, including those that are serious, will be graded by the investigator as follows:

Mild (Grade 1): awareness of event but easily tolerated

Moderate (Grade 2): discomfort enough to cause some interference with usual activity

Severe (Grade 3): inability to carry out usual activity

Very Severe (Grade 4): debilitating; significantly incapacitates subject despite symptomatic therapy.

The following categories and definitions of causal relationship to investigational product as determined by a physician should be used:

**Related:** There is a reasonable causal relationship to investigational product administration and the adverse event.

**Not Related:** There is not a reasonable causal relationship to investigational product administration and the adverse event.

The expression “reasonable causal relationship” is meant to convey in general that there are facts (eg, evidence such as de-challenge/re-challenge) or other arguments to suggest a positive causal relationship.

## 6.7 Collection and Reporting

Adverse events can be spontaneously reported or elicited during open-ended questioning, examination, or evaluation of a subject. To prevent reporting bias, subjects should not be questioned regarding the specific occurrence of one or more adverse events.

If known, the diagnosis of the underlying illness or disorder should be recorded, rather than its individual symptoms. The following information should be captured for all AEs: onset, duration, intensity, seriousness, relationship to investigational product, action taken, and treatment required. If treatment for the event was administered, it should be recorded in the medical record. The investigator must supply BMS and the IRB/IEC with any additional information requested, notably for reported deaths of subjects.

Completion of supplemental CRFs may be requested for AEs and/or laboratory abnormalities that are reported/identified during the course of the study.

### 6.7.1 Serious Adverse Events

Following the subject's written consent to participate in the study, all SAEs must be collected, including those thought to be associated with protocol-specified procedures. Collection of all SAEs must continue for 30 days after the last administration of the investigational product. If applicable, SAEs must be collected that relate to any later protocol-specified procedure. The investigator should notify BMS of any SAE occurring after this time period that is believed to be related to the investigational product or protocol-specified procedure.

All SAEs, whether considered related or unrelated to abatacept, must be reported to BMS (by the investigator or designee) within 24 hours of study personnel becoming aware of the event. If only limited information is initially available, follow-up reports are required. The original SAE form must be kept on file at the study site.

All SAEs should be faxed or emailed to BMS at:

**Global Pharmacovigilance & Epidemiology**  
**Bristol-Myers Squibb Company**  
**[contact]**  
**Email: [[contact]](mailto:[contact])**

For studies conducted under an **Investigator IND**, any event that is both serious and unexpected must be reported to the Food and Drug Administration (FDA) as soon as possible **and no later than 7 days** (for a death or life-threatening event) **or 15 days** (for all other SAEs) **after the investigator's or institution's initial receipt of the information**. BMS will be provided with a

simultaneous copy of all adverse events filed with the FDA. SAEs should be reported on MedWatch Form 3500A, which can be accessed at:  
<http://www.accessdata.fda.gov/scripts/medwatch/>.

**Bristol-Myers Squibb Company**  
**[contact]**  
**Email: [[contact]](mailto:[contact])**

Serious adverse events, whether related or unrelated to abatacept, must be recorded on the SAE page and reported within 24-hours to BMS (or designee) to comply with regulatory requirements. An SAE report should be completed for any event where doubt exists regarding its status of seriousness.

All SAEs must be reported within 24-hours by confirmed facsimile transmission (fax) and mailing of the completed SAE page. In some instances where a facsimile machine is not available, overnight express mail may be used. If only limited information is initially available, follow-up reports are required. (Note: Follow-up SAE reports should include the same investigator term(s) initially reported.) In selected circumstances, the protocol may specify conditions that require additional telephone reporting.

If the investigator believes that an SAE is not related to the investigational product but is potentially related to the conditions of the study (such as withdrawal of previous therapy, or a complication of a study procedure), the potential relationship should be specified in the narrative section of the SAE report.

If an ongoing SAE changes in its intensity or relationship to the investigational product, a follow-up SAE report should be sent within 24 hours to BMS. As follow-up information becomes available it should be sent within 24 hours using the same procedure used for transmitting the initial SAE report. All SAEs should be followed to resolution or stabilization.

## **6.7.2 Handling of Expedited Safety Reports**

In accordance with local regulations, BMS will notify investigators of all SAEs that are suspected (related to the investigational product) and unexpected (ie, not previously described in the Investigator Brochure). In the European Union, an event meeting these criteria is termed a

Suspected Unexpected Serious Adverse Reaction (SUSAR). BMS will send investigators an expedited safety report (ESR) to notify them of such an event.

Other important findings that BMS may report as ESRs include increased frequency of a clinically significant expected SAE, an SAE considered associated with study procedures that could modify the conduct of the study, lack of efficacy that poses significant hazard to study subjects, clinically significant safety findings from a nonclinical (eg, animal) study, important safety recommendations from a study data monitoring committee, or the decision by BMS to end or temporarily halt a clinical study for safety reasons.

Upon receiving an ESR from BMS, the investigator must review and retain the ESR with the Investigator Brochure. Where required by local regulations or when there is a central IRB/IEC for the study, BMS will submit the ESR to the appropriate IRB/IEC. The investigator and IRB/IEC will determine if the informed consent requires revision. The investigator should also comply with the IRB/IEC procedures for reporting any other safety information.

In addition, BMS will report suspected serious adverse reactions (whether expected or unexpected) to the relevant health authorities in all concerned countries according to local regulations (either as expedited and/or in aggregate reports).

### **6.7.3 Nonserious Adverse Events**

The investigator will begin collecting nonserious adverse event (NSAE) information once administration of the investigational product is initiated.

All identified NSAEs must be recorded and described in the medical record. If an ongoing NSAE worsens in its intensity, or if its relationship to the investigational product changes, a new NSAE entry for the event should be completed. NSAEs should be followed to resolution or stabilization, or reported as SAEs if they become serious. Follow-up is also required for NSAEs that cause interruption or discontinuation of investigational product, or those that are present at the end of study participation. Subjects with NSAEs at study completion should receive post-treatment follow-up as appropriate.

## **6.8 Laboratory Test Abnormalities**

All laboratory test results captured as part of the study should be recorded following institutional procedures. When reporting a test result that constitutes an adverse event, the clinical term should be used; for example, the event should be reported as “anemia” not “low hemoglobin.” Test results that constitute SAEs should be documented and reported as such.

## **6.9 Overdose**

An overdose is defined as the accidental or intentional ingestion or infusion of any dose of a product that is considered both excessive and medically important. All occurrences of overdose must be reported as an SAE.

## 6.10 Pregnancy

Sexually active WOCBP must use an effective method of birth control during the course of the study, in such a manner that the risk of failure is minimized. (See Section 4.2.1 for the definition of WOCBP.) Before enrolling WOCBP in this study, investigators must review the BMS-provided information about study participation for WOCBP, which can also be found in the GCP Manual for Investigators. The topics include the following:

General Information

Informed Consent Form

Pregnancy Prevention Information Sheet

Drug Interactions with Hormonal Contraceptives

Contraceptives in Current Use

Guidelines for the Follow-up of a Reported Pregnancy.

Before study enrollment, WOCBP must be advised of the importance of avoiding pregnancy during study participation and of the potential risk factors for an unintentional pregnancy. The subject must sign an informed consent form documenting this discussion.

### 6.10.1 Requirements for Pregnancy Testing

**All WOCBP MUST have a negative pregnancy test within 72 hours before receiving abatacept.** The minimum sensitivity of the pregnancy test must be 25 IU/L or equivalent units of HCG. If the pregnancy test is positive, the subject must not receive abatacept and must not continue in the study.

**In addition, all WOCBP must be instructed to contact the investigator and/or other study personnel immediately if they suspect they might be pregnant (eg, missed or late menstrual period) at any time during study participation.**

### 6.10.2 Reporting of Pregnancy

If, following initiation of the investigational product, it is subsequently discovered that a study subject is pregnant or may have been pregnant at the time of investigational product exposure, including during at least 6 half-lives after administration, the investigational product will be permanently discontinued in an appropriate manner (eg, dose tapering if necessary for subject safety). The investigator must immediately notify BMS of this event and record the pregnancy on the Pregnancy Surveillance Form (not on an SAE form). Initial information on a pregnancy must be reported immediately to BMS, and information on the outcome provided once it is available. Completed Pregnancy Surveillance Forms must be forwarded to BMS according to SAE reporting procedures.

**Note:** Any pregnancy that occurs in a female partner of a male study subject must be reported to BMS using the Pregnancy Surveillance Form.

Protocol-required procedures for study discontinuation and follow-up must be performed for the subject unless contraindicated by pregnancy (eg, x-ray studies). Other appropriate pregnancy follow-up procedures should be considered if indicated. Information regarding the course of the pregnancy, including perinatal and neonatal outcome, must be reported to BMS on the Pregnancy Surveillance Form. Infants should be followed for a minimum of 8 weeks.

## **6.11 Other Safety Considerations**

Any significant worsening noted during interim or final physical examinations, electrocardiograms, x-rays, and any other potential safety assessments, whether or not these procedures are required by the protocol, should also be recorded in the medical record.

## **7 STATISTICAL CONSIDERATIONS**

### **7.1 Sample Size Determination**

Based on two recently completed randomized trials (Price et al, 2008; Strober et al, 2009) in similar patient populations (moderate to severe AA) we expect placebo response rates to be between 6% (>50% improvement in SALT score) and 12% (>25% improvement). We have chosen our primary endpoint conservatively (proportion of patients with >50% improvement in SALT index) as a relatively strict criteria that should minimize spontaneous remission rates to 10% or less (0-2 of 15 subjects). This allows a higher degree of confidence that appreciable response rates are attributable to drug rather than spontaneous remission.

Assuming a historically known placebo response rate of 10% and the usual 5% level of significance (alpha), the sample size of 15 would provide 80.7% power to detect a difference of 30% in the response rate between the experimental treatment group and the historical placebo group.

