| 
Statistics:
 | 
This is a small exploratory open label pilot study to identify an efficacy signal in alopecia areata.
 
Based on two recently completed randomized trials (Strober et al, 2008; Price et al, 2009) in similar patient populations (moderate to severe AA) we expect placebo response rates to be between 6% (>50% improvement in SALT score (Olsen et al, 1999)) and 12% (>25% improvement). We have chosen our primary endpoint conservatively (proportion of patients with >50% improvement in SALT index) as a relatively strict criteria that should minimize placebo response rates to 10% or less (0-2 of 15 subjects). This allows a higher degree of confidence that appreciable response rates are attributable to drug rather than spontaneous remission.
 
Power analysis. Assuming a historically known placebo response rate of 10% and the usual 5% level of significance (alpha), the sample size of 15 would provide 80.7% power to detect a difference of 30% in the response rate between the experimental treatment group and the historical placebo group.
 
Since this is a small open label proof of concept study, we recognize that it will likely lack adequate power to conclusively demonstrate small efficacy signals (particularly if the assumed detectable difference of 30% is not met). Yet, descriptive summaries of all the primary and secondary efficacy outcomes (proportions for binary outcomes, means for continuous outcomes) will provide a preliminary indication of the effect size (even if smaller than 30%) that will aid design of subsequent efficacy trials.
 
Differences in the incidence of regrowth between patients with patch type AA vs patients with alopecia totalis or universalis will also be analyzed on an exploratory basis. In addition, response to abatacept treatment will be examined on an exploratory basis for correlation with the presence or absence of the AA GWAS risk haplotype.
 
To assess safety as a secondary endpoint, we will summarize via descriptive statistics, the occurrence of adverse events for the study group.
 
Accrual projections. The Dermatology clinic and private practice at CUMC currently sees 600 AA patients yearly, of which we anticipate 20-30% would be eligible (>40% hair loss). Accrual will be greatly facilitated by targeted recruitment through our existing NAAF registry which includes 400 AA patients in the New York area, the majority of which have patchy type disease. Thus, complete accrual of 15 subjects should be feasible within 1 year from a pool of >100 eligible subjects yearly.
 |

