### **7.3 Endpoint Definitions**

1. Proportion of patients with >50% improvement in SALT index at 24 weeks

2. Percent hair regrowth from baseline determined by SALT measurements following 12, 24 weeks of treatment and at weeks 36 and 48 following discontinuation of treatment.
3. Comparison of the proportion of responders in the experimental group with the historically known placebo response rate (<10%), with response defined as 50% change in SALT score (50% regrowth) from baseline, at weeks 12, 36 and 48.
4. Comparison of the proportion of subjects in the experimental group and the proportion of subjects in the historical control group attaining global overall improvement SALT score of A5 (100% coverage) supported by  $\leq$  SALT 25 at weeks 12, 24, 36 and 48.
5. Change in PGA (Physician Global Assessment) based on evaluation of live evaluations and standardized photographs between baseline, week 12, 24, 36 and 48.
6. Change in patient global assessment between baseline, weeks 12, 24, 36, and 48.
7. Change in patient quality of life assessment from baseline to weeks 12, 24, 36, and 48.
8. Frequency of occurrence and timing of relapse (as defined above) in responders followed for 6 months off therapy.
9. To assess safety, we will summarize the incidence of adverse events for the study group.

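### Section 7.1 and the synopsis equate a spontaneous response of 10% or less with 0-2 of 15 subjects, but 2/15 is 13.3% and 3 or more responders arise in 18.4% of trials at a true 10%

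*Combined protocol and SAP*

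**What the plan says.** - **Section 7.1, historical rates:** "we expect placebo response rates to be between 6% (>50% improvement in SALT score) and 12% (>25% improvement"). The first of these matches the primary endpoint.
- **Section 7.1, the count:** the chosen criterion "should minimize spontaneous remission rates to 10% or less (0-2 of 15 subjects"). The Statistics part of the synopsis says the same of placebo response: it "should minimize placebo response rates to 10% or less (0-2 of 15 subjects").
- **Section 7.1, the inference, in the next sentence:** "This allows a higher degree of confidence that appreciable response rates are attributable to drug rather than spontaneous remission".
- **Section 7.1, power:** the calculation takes a fixed historical rate of 10% and a 5% alpha, and its stated result is that "the sample size of 15 would provide 80.7% power to detect a difference of 30% in the response rate". No test, sidedness or critical number of responders is given.
- **Section 7.3:** item 1 is the week-24 responder proportion. Item 3 compares later and earlier responder proportions with the "historically known placebo response rate (<10"%), again without a test.
- **Section 7.4.3:** efficacy is to be summarised descriptively, with proportions for binary outcomes. No interval is named.

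**The concern.** The parenthesis can be read in two ways, and neither works. As a conversion of the rate into subjects, it overshoots, because the largest whole count at or below 10% of 15 is 1. As the range of counts to expect when the true rate is 10%, it leaves out nearly one trial in five.

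The slip matters because of where it stands. The trial has a single arm, so responders can be judged only against what would have happened without drug. The sentence after the count moves straight to attributing response to the drug. The plan gives no critical count and no confidence interval that would correct a reader who takes 0-2 as the extent of spontaneous remission. Such a reader would see 3 or 4 responders as outside it. Section 1.5 says a positive result would be the basis for designing larger randomised trials, so an over-reading would carry forward into them.

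**Working it through.** **Inputs.** n = 15; p0 = 0.10 and alpha = 0.05 (Section 7.1); p1 = 0.10 + 0.30 = 0.40 (Section 7.1); expected rate for >50% improvement = 0.06 (Section 7.1); count range 0-2 (Section 7.1 and synopsis).

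**1. The plan's power figure.** The test is not named, so several one-sample calculations against a fixed 10% were tried.
- Two-sided arcsine: h = 2·asin(√0.40) − 2·asin(√0.10) = 0.726; power = Φ(h·√15 − 1.96) = Φ(2.81 − 1.96) = 80.3%.
- Two-sided normal with continuity correction: SE0 = √(0.10·0.90/15) = 0.0775; SE1 = √(0.40·0.60/15) = 0.1265; power = Φ[(0.30 − 1.96·0.0775 − 1/30)/0.1265] = 81.8%.

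Both lie close to the stated 80.7%, so the power statement is reproduced approximately and is not the error.

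**2. The conversion.** 0.10 × 15 = 1.5 subjects. 1/15 = 6.7%; 2/15 = 13.3%.

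**3. What a true 10% produces.** With P(X = x) = C(15, x)·0.10^x·0.90^(15−x), the probabilities of 0, 1 and 2 responders are 0.2059, 0.3432 and 0.2669, so P(0-2) = 0.8159. Each upper tail follows by subtraction (unrounded values used). The intervals are Clopper-Pearson: lower limit the 2.5% point of Beta(x, 16 − x), upper limit the 97.5% point of Beta(x + 1, 15 − x).

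| Responders x | Observed rate | P(X ≥ x) at true 10% | Exact 95% CI | Includes 10%? |
|---|---|---|---|---|
| 3 | 20.0% | 18.4% | 4.3%-48.1% | yes |
| 4 | 26.7% | 5.6% | 7.8%-55.1% | yes |
| 5 | 33.3% | 1.3% | 11.8%-61.6% | no |

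**4. At the expected 6%.** P(0), P(1) and P(2) are 0.3953, 0.3785 and 0.1691, so P(X ≥ 3) = 1 − 0.9429 = 5.7%.

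**5. The first count that excludes 10%.** Five of 15 is the smallest count with an exact one-sided error at or below 5%; it is also below 2.5%. Its error is 1.27%, and P(X ≥ 5) at a true 40% is 78.3%.

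**6. Sensitivity to AT/AU patients.** The plan allows 2 to 5 patients with current alopecia totalis or universalis and calls spontaneous regrowth there extremely rare. Assume they never remit and the others remit at 10%. Then n is effectively 13 to 10, and P(X ≥ 3) is about 13% to 7%.

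**The case against.** **No decision rule is broken.** The documents never say that 3 of 15 is a signal. The quantified target is a 30-point gain over 10%, which is 40% or 6 of 15. An exact test at the stated 5% would credit neither 3 nor 4 responders. An uncorrected two-sided z-test would not credit 3 (z = 0.10/0.0775 = 1.29), though it would credit 4 (z = 0.1667/0.0775 = 2.15, p = 0.031). This stands: a reader might infer that the plan would declare success above 2 responders, and the documents do not support that.

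**The slip is half a subject.** The 0-2 may be a loose rounding of 1.5. That is plausible, but the text attaches it to a rate of 10% or less and builds on it, so it should still be right.

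**The 18.4% applies at the ceiling.** It does. At 6% the figure is 5.7%, and AT/AU enrolment would lower it as in step 6. The 10% is nevertheless the plan's own planning value.

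**Other readings that go too far.**
- One might call the comparison rate inconsistent, since 6%, 10% and below 10% all appear. Section 7.1 gives 6% as the expectation and 10% as the planning value. A rate below 10% fits 10% as an upper bound, testable at its boundary. Nothing proposes a test against 6%.
- One might use 12% as a spontaneous rate here. Section 7.1 ties it to >25% improvement, not to the primary endpoint.
- One might say the efficacy conclusion rests on this count alone. The study is an exploratory pilot with continuous SALT change, global assessments and relapse also planned, and Section 7.4.3 admits its limited power.

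**Conclusion.** The stated equivalence is wrong in both places: 2/15 is 13.3%, and at a true 10% the range 0-2 misses 18.4% of trials. The consequence is conditional. Because the plan offers no other responder count for spontaneous remission and no interval, 3 or 4 responders could be over-read, although exact 95% intervals for both include 10%. The size of that risk depends on the true spontaneous rate: 18.4% for 3 or more at 10%, 5.7% at 6%. These figures assume 15 evaluable, independent subjects with a common rate. The sample size and the 80.7% power figure are not in question, and the point concerns interpretation rather than conduct or safety.

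**What to change.** 1. In Section 7.1 and in the synopsis, replace the parenthesis on 0-2 of 15 subjects with: *expected 1.5 of 15; at a true 10% rate, 3 or more occur in 18.4%, 4 or more in 5.6% and 5 or more in 1.3% of such trials*.
2. In Section 7.4.3, report the week-24 responder proportion with its exact (Clopper-Pearson) 95% confidence interval, set against the 10% already assumed in Section 7.1.
3. In the same place, note that 5 of 15 is the smallest count whose exact interval excludes 10%, with a one-sided error of 1.3% and a power of 78.3% at a true 40%.

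The cost is wording and one interval. The benchmark becomes slightly less favourable to the drug, and the exact power is a little under the stated 80.7%. Patients, visits, treatment and sample size are unaffected.
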